7.2.3 St Georges Respiratory Questionnaire (SGRQ)

The total SGRQ score and component scores (symptoms, activity and impact scores) will be calculated according to the SGRQ scoring manual. Total score as well as the component scores will be summarized by treatment and visit. Corresponding mean and CI plots over time will be provided as well as a listing by subject and visit. The listing will contain both response to the individual questions in SGRQ as well as the total and component scores.

7.2.4 Whole Lung Lavage

The number of subjects experiencing whole lung lavage (WLL), and the number of WLLs events will be summarized by visit and overall. The summary will also include event rates (95% CI) adjusted for time in trial since visit 1. A separate summary will present the number of subjects and the number of events between IMPALA and IMPALA-X. A WLL event is defined as a WLL procedure performed on a unilateral lung. These events are entered at visit 1 as part of the overall clinical assessment.

Time in trial is defined as the number of days from visit 1 to end of trial date.

Event rates shown as the number of events per subject year and the 95% confidence intervals (CI) of the event rates are estimated using a negative binomial model.

The 95% CI will be estimated using the below piece of code in SAS. Here the dataset *wll_rate* has the number of whole lung lavage by subject in parameter *aval*, and the logarithm of the time of exposure in parameter called *log_dur*. The parameter one has the value 1 (one) for all subjects. The dataset final include the estimated rate (*esti*), and the lower limit of the confidence interval (*lowci*) and the upper limit of the confidence interval (*uppci*).

```
ods output ParameterEstimates=ParameterEstimates;

proc genmod data= wll_rate;

class one;

model aval= one /cl noint dist=negbin offset=log_dur link=log ;

lsmeans one / exp cl;

run;

data exp;

set ParameterEstimates;

where parameter="one";

esti = exp(estimate); * estimate;

lowci = exp(LowerWaldCL); * lower limit of confidence interval;

uppci = exp(UpperWaldCL); * upper limit confidence interval;

run;
```

Furthermore, the whole lung lavage will be summarized by location (left, right or both) and the volume of saline used will be summarized.

A listing of subjects requiring WLL including reasons for WLL, date of criteria met, and date of procedure will be provided.

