3.2 Trial Design

The trial is an open-label, non-controlled, multi centre clinical trial of inhaled molgramostim in autoimmune pulmonary alveolar proteinosis (aPAP) patients.

Subjects with aPAP who have completed the IMPALA (MOL-PAP-002) trial will be eligible for this trial.

At the baseline visit, eligible subjects may continue or re-start treatment with inhaled molgramostim (300 µg) administered intermittently in cycles of seven days molgramostim, administered once daily, and seven days off treatment.

Trial visits will be conducted at 6-monthly intervals until the end of trial. Participating subjects will be encouraged to contact the clinic between visits if they experience adverse events (AEs) or worsening of aPAP, or if they have any other concerns.

During the trial, Whole Lung Lavage (WLL) will be applied as rescue therapy. The criterion for performing WLL is clinical worsening of aPAP based on symptoms, reduced exercise capacity and/or findings of hypoxemia or desaturation according to the investigator's judgement. The reason(s) for conducting WLL will be documented. Subjects undergoing WLL will continue treatment with molgramostim, unless discontinuation is medically required, according to investigator's discretion.

Subjects may discontinue molgramostim due to remission of aPAP, lack of response that requires a different treatment modality, or AEs. Subjects becoming pregnant will be required to discontinue treatment with molgramostim. Subjects who discontinue molgramostim will be encouraged to continue in the trial and attend visits according to the same schedule until end of the trial. Molgramostim treatment may be re-started if medically required. Subjects not requiring treatment at the Baseline visit may start molgramostim treatment during the trial if medically required.

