Savara received advice on the MOL-PAP-002 trial results from EMA and FDA. The data demonstrated more favorable evidence of efficacy on the continuous dosing regimen. Following the advice Savara has subsequently decided to conduct an additional Phase III confirmatory trial to support future registration of the continuous dosing regimen. The SAV006-03 trial investigates an intermittent dosing regimen but considering the MOL-PAP-002 clinical trial results and the received health authority advice there will not be adequate efficacy and safety data on the intermittent dosing regimen to support a marketing authorization application for this regimen. Consequently, Savara has decided to discontinue the SAV006-03 trial and support the continued clinical investigation of the continuous dosing regimen in a new trial.

60 subjects have been enrolled in the SAV006-03 trial and enrolled subjects will be able to continue treatment until end of 2020. Of these, 55 subjects are on active treatment and 5 subjects do not receive treatment at the time of trial termination. The 5 subjects have been allowed to remain in the trial to observe development of their disease without receiving treatment.

The data from the SAV006-03 trial will be included in the ongoing safety evaluation of molgramostim nebulizer solution. The results of the SAV006-03 trial will also be included as part of a potential future marketing authorization application for use of molgramostim nebulizer solution as a potential treatment for autoimmune pulmonary alveolar proteinosis, although the intermittent dosing regimen will likely not be included as a treatment regimen under posology.

All generated data will be cleaned and assessed according to plan and will contribute to the risk-benefit profile for molgramostim. The trial will be reported according to ICH GCP requirements.

Table 1 Activities flow chart

Table 1: Visit	Visit 1	Visit 2	Visit 3	Visit 4	Visit 5	Visit 6	Visit 7	FU TC	Unscheduled
	Baseline ^a	Month 6	Month 12	Month 18	Month 24	Month 30	Month 36	2 wks after trial completion	
Time	0	Week 26	Week 52	Week 78	Week 104	Week 130	Week 156		
Visit Window	N/A	± 4wks	± 4 wks	± 4 wks	± 4 wks	± 4 wks	± 4 wks	+ 1 wk	
Informed consent	X								
Eligibility criteria	X								
Demographics	X								
Concomitant medication	X	X	X	X	X	X	X		X
WLL information ^b	X	X	X	X	X	X	X		X
Pregnancy test and contraceptive check ^c	X	X	X	X	X	X	X		(X) ^d
Physical Exam	(X)		X		X		X		(X) ^d
Vital signs	(X)	X	X	X	X	X	X		(X) ^d

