6.1 Exposure

Treatment with molgramostim at least once during the trial (yes/no) will be summarized by treatment.

Exposure will be summarized by treatment showing summary statistics (mean, standard deviation, median, p25, p75, minimum and maximum).

Furthermore, an output will be generated showing number of subjects with ≥ 6 months exposure, ≥ 12 months exposure, ≥ 18 months exposure etc.

Exposure will be defined as number of days from visit 1 to last kit date + 21 days or end of trial date whatever comes first.

For the safety update (see section 8.2) exposure will be calculated as number of days from visit 1 to Last kit date + 21 days or Date of last visit before cut-off for safety update whatever comes first.

Relative exposure will be defined as

$$\text{Relative exposure} = \text{Exposure} / \text{number of days in trial}$$

where exposure is defined above. Relative exposure will be summarized by treatment and listed.

Due to premature trial closure a table with last visit attended will be presented showing number of patients and percentages. For patients where the last visit was entered as visit 7, the original visit they came in for will be presented in this table based on full analysis set. A listing of visits attended will be presented.

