- Listing 16.2.6.8 Individual overall clinical assessments (all subjects)
- Listing 16.2.6.9 Individual GM-CSF measurements above lower level of quantification (all subjects)
- Listing 16.2.7.1 Adverse events (all subjects)
- Listing 16.2.7.2 Serious adverse events (all subjects)

Listing 16.2.7.3 Adverse drug reactions (all subjects)

Listing 16.2.7.4 Adverse events leading to treatment discontinuation (all subjects)

Listing 16.2.8.1 Individual haematology (all subjects)

Listing 16.2.8.2 Individual clinical chemistry (all subjects)

Listing 16.2.9.1 Individual vital signs (all subjects)

Listing 16.2.9.2 Individual electrocardiogram (all subjects)

Listing 16.2.10.1 Individual CT scans (all subjects)

13 List of Tables

Section 14.1

Table 14.1.1 Subject disposition (full analysis set)

Table 14.1.2 Number of subjects by visit (full analysis set)

Table 14.1.3 Baseline demographics (full analysis set)

Table 14.1.4 Medical history (full analysis set)

Table 14.1.5 Summary of exposure (months) (safety analysis set)

Table 14.1.6 Summary of cumulative exposure (safety analysis set)

Table 14.1.7 Summary of relative exposure (safety analysis set)

Table 14.1.8 Summary of last visit attended (full analysis set)

Table 14.1.9 Concomitant medication (safety analysis set)

Table 14.1.10. Summary of missed key secondary endpoints assessments due to COVID-19 pandemic (safety analysis set)

Table 14.1.11 Summary of alternative endpoint ascertainment due to COVID-19 pandemic (safety analysis set)

Section 14.2

(14.2.1: Blood gas analysis endpoints)

Table 14.2.1.1 Summary of (A-a)DO₂ (mmHg) (full analysis set)

Table 14.2.1.2 Summary of change from baseline in (A-a)DO₂ (mmHg) (full analysis set)

(14.2.2: 6 minutes walking test endpoints)

Table 14.2.2.1 Summary of 6 minutes walking distance (m) (full analysis set)

Table 14.2.2.2 Summary of change from baseline in 6 minutes walking distance (m) (full analysis set)

Table 14.2.2.3 Summary of pre-walk dyspnoea score (Borg CR10) (full analysis set)

Table 14.2.2.4 Summary of change from baseline in 6 minutes walking distance (m) (full analysis set)

Table 14.2.2.5 Summary of post-walk dyspnoea score (Borg CR10) (full analysis set)

Table 14.2.2.6 Summary of change from baseline in dyspnoea score (Borg CR10) (full analysis set)

Table 14.2.2.7 Summary of SpO₂ at start of walk (%) (full analysis set)

Table 14.2.2.8 Summary of change from baseline in SpO₂ at start of walk (%) (full analysis set)

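### The whole lung lavage rate has two conflicting denominators in SAP 7.2.4, and its tables use the safety set although efficacy summaries belong to the full analysis set

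*SAP*

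**What the plan says.** **Denominator, text.** SAP 7.2.4: "The summary will also include event rates (95% CI) adjusted for time in trial since visit 1". The definition follows: "Time in trial is defined as the number of days from visit 1 to end of trial date". Rates are per subject year, from a negative binomial model.

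**Denominator, code description.** The same section explains the input dataset as holding the number of lavages per subject "and the logarithm of the time of exposure in parameter called" log_dur, which is the model offset. The code shown does not derive log_dur.

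**Exposure.** SAP 6.1: "Exposure will be defined as number of days from visit 1 to last kit date + 21 days or end of trial date", whichever comes first. The section then divides exposure by days in trial to form relative exposure, "where exposure is defined above. Relative exposure will be summarized by treatment and listed". The list of tables in SAP 13 gives that ratio its own output, Table 14.1.7.

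**Follow-up after stopping drug.** SAP 3.2: "Subjects who discontinue molgramostim will be encouraged to continue in the trial". On status at closure, for the 60 enrolled: "Of these, 55 subjects are on active treatment and 5 subjects do not receive treatment at the time of trial termination".

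**Analysis set.** SAP 4 uses the full analysis set for demographics and efficacy summaries, and the safety set (subjects with exposure in this trial) for safety summaries. Protocol 11 includes all subjects in all presentations. WLL frequency is a secondary endpoint in SAP 7.2 and sits under Efficacy Assessments in Protocol 10.7. Yet Tables 14.2.4.1 to 14.2.4.4 are all labelled safety analysis set.

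**The concern.** A rate needs events and person-time from the same window. SAP 7.2.4 counts lavages by visit and overall, with no on-treatment restriction; adverse events, by contrast, are limited to a treatment-emergent window in SAP 8.1.2. If the offset is exposure as Section 6.1 defines it, a subject who stops drug but stays in the trial contributes every lavage but only part of the follow-up. A programmer who follows the code description would report a different quantity from the one the text defines.

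The table labels remove subjects never treated in this trial. SAP 9 says there are some, and Section 4 states no exception for WLL. The restriction is hardest to explain for Table 14.2.4.1, which counts lavages between the two trials, before any exposure in this one.

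The two points are linked. A never-treated subject has no kit date, so an exposure-based log_dur does not exist, and a record with a missing offset drops out of the model. Changing only the table labels would not bring these subjects into the modelled rate.

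Requirement for WLL is a stated secondary objective. With no control group, the result will be read as an absolute rate per subject year, so its denominator and population define what is reported.

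**Working it through.** The plan states no WLL rate or count, so there is no figure to reproduce. The check compares the definitions and then bounds the effect on the crude rate (events divided by subject-years).

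**1. The definitions side by side**

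| Place in SAP | Term | Ends at |
|---|---|---|
| 7.2.4, text | time in trial | end of trial date |
| 7.2.4, code description | time of exposure | not stated there |
| 6.1 | exposure | earlier of last kit date + 21 days and end of trial date |
| 8.2, WLL in the safety update | subject years | cut-off date |

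Exposure and time in trial both start at visit 1, and exposure is never the longer. Section 6.1 reports their ratio, so the SAP does not treat them as synonyms. Section 8.2 supports follow-up time as the intent, but only weakly: the rate table, 14.2.4.2, is not among the safety-update outputs. The explicit definition in 7.2.4 is the stronger evidence.

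**2. Denominator effect**

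With the same events, rate(exposure) / rate(time in trial) = 1 / (pooled relative exposure).

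- Relative exposure 0.95: 1/0.95 = 1.05
- 0.90: 1/0.90 = 1.11
- 0.80: 1/0.80 = 1.25

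To set a scale, take 55 subjects on drug and 5 off drug. Assume equal follow-up and that last kit date means the last kit used. Let f be the share of follow-up for which the 5 were off drug.

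Relative exposure = (55 + 5(1 − f)) / 60

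- f = 0.5: 57.5/60 = 0.958, factor 1.04
- f = 1 (limit): 55/60 = 0.917, factor 1.09

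The SAP does not define last kit date. If it meant the last 6-monthly dispensing visit, exposure would end 182 − 21 = 161 days before the final visit even for a subject dosed throughout. The factor would be T/(T − 161), with T in days:

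- Final visit at week 52: 364/203 = 1.79
- Final visit at week 156: 1092/931 = 1.17

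These larger factors depend wholly on that reading.

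**3. Population effect**

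Let u of the 60 be never treated, with WLL rate r times that of treated subjects, and equal follow-up.

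Safety-set rate / full-set rate = 60 / (60 − u + u·r)

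| u | r = 0 | r = 1 | r = 2 |
|---|---|---|---|
| 5 | 60/55 = 1.09 | 60/60 = 1.00 | 60/65 = 0.92 |
| 1 | 60/59 = 1.02 | 60/60 = 1.00 | 60/61 = 0.98 |

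The number never treated is not stated. On the 55/5 split it is at most 5.

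**4. The two effects together**

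The same 5 subjects drive both, so the two factors of 1.09 do not multiply. If u of the 5 were never treated and had no WLL, and the other 5 − u were off drug for share f, the combined ratio is 60 / (55 + (5 − u)(1 − f)). This cannot exceed 60/55 = 1.09.

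**The case against.** The strongest reply is that time of exposure is ordinary language for person-time in a rate model. The text states and defines time in trial just before the code, the variable is called log_dur, and the phrase does not refer to Section 6.1. That is probably what the authors meant. It does not settle the matter: exposure is a defined term in this SAP, and the phrase is the only instruction for building log_dur.

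On the population, one can argue that the objective concerns WLL during long-term use of the drug, so subjects never dosed here do not inform it. But the oxygenation, exercise, quality-of-life and lung-function objectives carry the same wording, and their tables use the full analysis set. SAP 9 explains why a safety set was added, not why WLL should use it.

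It is fair that the missing offset for never-treated subjects arises only once the tables move to the full set. It is a reason to make both edits together, not a separate defect.

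The consequence is also limited. Reporting is descriptive, SAP 3.2 says the data will not adequately support an application for this regimen, and Listing 16.2.6.4 shows lavages for all subjects. Sampling error will be larger than the shift. Assume 60 subjects, 1.75 years each, 0.25 lavages per year and dispersion 1. The mean count is 0.25 × 1.75 = 0.4375, and the relative standard error is √[(0.4375 + 0.4375²)/60] / 0.4375, about 23%. This bears on priority. It does not make the two definitions agree.

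**Conclusion.** The concern holds on both counts. SAP 7.2.4 names two different person-times for one rate, and the four WLL tables depart from the rule in Section 4 without a stated reason. This should be corrected.

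The size is probably modest. The exposure offset inflates the crude rate by about 1.04 to 1.09 if the 5 untreated subjects were off drug for between half and all of their follow-up. The safety set changes it by a factor of 0.92 to 1.09, in an unknown direction. Both ranges assume equal follow-up; the first also assumes that the 55 were dosed to the end and that last kit date is the last kit used. They are ratios of crude rates, so they indicate scale and do not strictly bound the negative binomial estimate. The documents do not allow a firmer figure.

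**What to change.** In SAP 7.2.4, define log_dur as log(time in trial / 365.25), with time in trial as already defined there, and delete the reference to time of exposure. The division is needed because time in trial is in days and the rate is per subject year.

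Run Tables 14.2.4.1 to 14.2.4.4 on the full analysis set. If a treated-only rate is wanted, add it as a labelled supportive table on the safety set.

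Two small clarifications could go into the same edit; the finding does not depend on them. Confirm that location both counts as two events under the unilateral-lung definition. Either add a descriptive time to first WLL, which Protocol 11.2 lists, from the procedure dates already listed, or declare its omission in SAP 9.

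The cost is one phrase and one offset variable, four table labels, and one sentence each in 7.2.4 and Section 9. No new data are needed.

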7.2.5 Lung Function Test

The percentage predicted values (DLCO (%), FEV1 (%) and FVC (%)) will be summarized by visit.

DLCO % predicted will be haemoglobin (Hb) corrected according to the formula:

$$DLCO (\% \text{ predicted, Hb corrected}) = 100 \times \frac{DLCO (\text{measured})}{DLCO(\text{absolute predicted}) \times 1.7Hb/(a + Hb)}$$

Where a is 10.22 for males and 9.38 for females, Hb must be measured in g/dL. Corresponding mean and CI plots over time will be provided.

All data will be listed including both actual and % predicted values of DLCO, FEV1 and FVC.

7.2.6 Disease Severity Score (DSS)

DSS will be summarized using N (%) in each category over time. Furthermore, a table showing number of subjects (N (%)) having improved/unchanged/worsened DSS score from visit 1 will be provided.

Assessment of DSS from subjects-visits where supplementary oxygen was used during arterial blood gas samples will be excluded from both summary tables.

A corresponding listing by subject and visit will be provided.

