10.7. Efficacy Assessments

10.7.1. Blood Gas Analysis

The following variables will be assessed from an arterial blood gas sample collected at the timepoints shown in [Table 1](#).

- PaO₂ (mmHg/kPa) – arterial partial pressure of oxygen
- PaCO₂ (mmHg/kPa) – arterial partial pressure of carbon dioxide
- F_iO₂ – fraction of inspired oxygen

P_{atm} (ambient atmospheric pressure) must be collected using a bedside barometer. The P_{H₂O} (saturated vapour pressure of water at body temperature) will be set to 47 mmHg / 6.266 kPa.

The Aa Gradient (A-a)DO₂ will be calculated centrally using the following formula:

$$Aa \text{ Gradient} = \left(F_i O_2 (P_{atm} - P_{H_2O}) - \frac{P_a CO_2}{0.8} \right) - P_a O_2$$

Sites that are experienced in the use of capillary sampling for blood gas analysis as part of their standard care, may use this option instead of an arterial blood gas sample.

Subjects should rest for at least 10 minutes before puncture and the sample should be taken in supine position. Trial specific instructions will be provided in a separate document. The sample will be analysed in accordance with local routines.

If possible, arterial blood gases should be conducted with the subject breathing room air. If the subject cannot tolerate temporary discontinuation of supplemental oxygen during blood gas sampling, blood gas sampling at subsequent visits should, if possible, be conducted using the same oxygen flow rate as was used in IMPALA and kept constant during the trial.

10.7.2. 6-Minute Walk Test (6MWT)

Exercise capacity will be assessed using the 6MWT at the timepoints shown in [Table 1](#).

The 6MWT will be performed in accordance with European Respiratory Society/American Thoracic Society (ERS/ATS) guidance [[Holland 2014](#)] by technicians with documented training and experience of performing the 6MWT in accordance with the referred ERS/ATS guidance. The 6MWT should be performed twice at each visit in accordance with the ERS/ATS guidance.

Data from both tests should be entered in the eCRF. Parameters to be recorded comprise pre and post walk dyspnoea score using the Borg (CR-10) Dyspnea Score ([Appendix 4.1](#)) SpO₂ (%) at start, worst SpO₂ (%) during the walk, distance walked (6MWD; m), duration of the walk (minutes and seconds), oxygen flow rate if applicable, reason for stop ping early (if applicable).

Trial specific instructions for the 6MWT are provided in [Appendix 4.2](#).

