10.7.5. Disease Severity Score

The DSS will be assessed at the timepoints shown in [Table 1](#).

The DSS is based on the presence of symptoms and degree of reduction in PaO₂ determined with the individual breathing room air in the supine position [[Inoue 2006](#)].

The DSS is a 5-point score as follows:

1 = no symptoms and PaO₂ ≥ 70 mmHg

2 = symptomatic and PaO₂ ≥ 70 mmHg

3 = 60 mmHg ≤ PaO₂ < 70 mmHg

4 = 50 mmHg ≤ PaO₂ < 60 mmHg

5 = PaO₂ < 50 mmHg.

If possible, the blood gas assessment should be conducted with the subject breathing room air (see Section [10.7.1](#)). For subjects requiring supplemental oxygen during the blood gas assessment the DSS will be based on the PaO₂ obtained while breathing oxygen.

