11. STATISTICS

No formal sample size calculation was done as this is an open-label extension trial. Up to 90 subjects will be included.

Data will be summarised using summary statistics. Continuous data will be presented with the number of observations, mean value, standard deviation, minimum, quartile 1, median, quartile 3 and maximum value. Categorical data will be presented as counts and percentages. The data will be presented by visit in tables and graphs. Individual subject data will be listed. Further details of all analyses will be given in the statistical analysis plan.

No “analysis sets” (intention to treat, per protocol, etc.) are defined. All subjects will be included in the analyses/data presentations (equivalent to a Full Analysis Set).

Only recorded data will be analysed/presented and any subjects who have missing data will only have observed data reported, with no imputation for missing data.

Interim cuts of data may be done on a yearly basis and as needed for regulatory purposes (e.g. 120-day safety update).

Data listings will show all recorded data.

Data from the trial is planned to be combined with relevant data from the IMPALA trial; these combined analyses will be reported separately.

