7.2.1 Blood Gas Analysis

The following variables will be assessed from an arterial blood gas sample collected at the timepoints shown in Table 1.

- PaO₂ (mmHg) – arterial partial pressure of oxygen
- PaCO₂ (mmHg) – arterial partial pressure of carbon dioxide
- F_iO₂ – fraction of inspired oxygen

P_{atm} (ambient atmospheric pressure) must be collected using a bedside barometer. The P_{H₂O} (saturated vapor pressure of water at body temperature) will be set to 47 mmHg / 6.266 kPa.

The Aa Gradient (A-a)DO₂ will be calculated centrally using the following formula:

$$Aa\ Gradient = \left(F_i O_2 (P_{atm} - P_{H_2O}) - \frac{P_a CO_2}{0.8} \right) - P_a O_2$$

The Aa Gradient will be summarized by visit. A corresponding mean and with confidence interval (CI) plot over time will be provided. Subjects on supplementary oxygen during blood gas sample are excluded from the relevant visits in the summary.

A corresponding listing by subject and visit will be provided including all subjects regardless of use of supplemental oxygen.

Any Aa Gradients reported in kPa will be converted to a result in mmHg, this will be done using a factor $k=7.5$ ($kPa \times 7.5 = mmHg$).

7.2.2 6-minute Walk Test (6MWT)

Exercise capacity will be assessed using the 6MWT to measure the 6-minute walk distance (6MWD) at the timepoints shown in Table 1.

The 6MWT should be performed twice at each visit in accordance with the European Respiratory Society (ERS)/American Thoracic Society (ATS) guidance.

Data from both tests should be entered in the eCRF. Parameters to be recorded comprise pre and post walk dyspnea score using the Borg (CR-10) Dyspnea Score (including the difference post minus pre dyspnoea score), SpO₂ (%) at start, worst SpO₂ (%) during the walk, distance walked (m), duration of the walk (minutes and seconds), oxygen flow rate if applicable, reason for stopping early (if applicable). For each subject and each visit the results from the test with the longest distance walked will be used in the reporting of the trial.

Distance in meter, Borg score endpoints, and SpO₂ and the desaturation (first SpO₂-worst SpO₂) will be summarized by treatment and visit. Furthermore, number of subjects (N, %) who completed the test will be presented by treatment and visit.

A corresponding mean and CI plot over time as well as a corresponding listing by subject and visit will be provided for each of the endpoints.

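### DSS tables omit visits sampled on oxygen, contrary to protocol 10.7.5 and undeclared; moves onto or off oxygen have no place in the shift table, and PaO2 has no planned summary

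*SAP*

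**What the plan says.** Protocol 10.7.5 defines the five-point DSS from symptoms and PaO2, "determined with the individual breathing room air in the supine position". The same section then provides for the exception: "For subjects requiring supplemental oxygen during the blood gas assessment the DSS will be based on the" PaO2 measured on oxygen.

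SAP 7.2.6 plans two tables: DSS category over time (Table 14.2.6.1) and improved, unchanged or worsened against the start of the trial (Table 14.2.6.2). It adds: "Assessment of DSS from subjects-visits where supplementary oxygen was used during arterial blood gas samples will be excluded from both summary tables". SAP 7.2.1 treats (A-a)DO2 in the same way: "Subjects on supplementary oxygen during blood gas sample are excluded from the relevant visits in the summary". The (A-a)DO2 listing is kept complete, "including all subjects regardless of use of supplemental oxygen".

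Protocol 10.7.1 asks for room-air sampling where possible and has a fallback that begins: "If the subject cannot tolerate temporary discontinuation of supplemental oxygen during blood gas sampling". Such subjects are then sampled on oxygen, if possible at the flow rate used in IMPALA.

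Protocol 11 gives two general rules: "All subjects will be included in the analyses/data presentations (equivalent to a Full Analysis Set") and "The data will be presented by visit in tables and graphs". PaO2 is a secondary endpoint in protocol 5.3.2 and 11.2 and in SAP 7.2, and SAP 5.2 counts it among the key ones. SAP 2 sends the reader to SAP 9 for departures from the protocol's analysis. SAP 9 names two: the added safety analysis set and the unreported time off treatment.

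**The concern.** Whether a visit is left out depends on the patient's disease at that visit. A subject who worsens until oxygen cannot be paused for sampling leaves the DSS shift table. One who no longer needs it enters without a usable starting score. The three shift categories have no place for either, although these may be among the most informative changes in the trial. The by-visit (A-a)DO2 means have the same weakness: they describe whoever was sampled on room air, a group that can change between visits.

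Oxygenation is the first secondary objective listed. A reader of the DSS table cannot tell how many subjects are absent because they needed oxygen and how many for other reasons. The endpoint that measures oxygenation most directly, PaO2, is not summarised anywhere.

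**Working it through.** The plan gives no figure on this point, so there is none to reproduce. The check compares the texts and adds illustrations with stated assumptions.

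**1. Is there a conflict, and is it declared?** For DSS the conflict is explicit: protocol 10.7.5 produces a score for an on-oxygen visit, and SAP 7.2.6 removes that score from both tables. For (A-a)DO2 it is inferred: protocol 10.7.1 and 11 state no exclusion, and SAP 7.2.1 introduces one. Neither is among the two items in SAP 9.

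**2. What the two rules do to one subject.** Cut-offs for a symptomatic subject (protocol 10.7.5): PaO2 of 70 mmHg or more = 2; 60 to below 70 = 3; 50 to below 60 = 4; below 50 = 5. Start at 55 mmHg on room air (DSS 4), with the later sample taken on oxygen:

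| Later PaO2 on oxygen | DSS | Protocol 10.7.5 | SAP 7.2.6 |
|---|---|---|---|
| 75 | 2 | improved | no entry |
| 65 | 3 | improved | no entry |
| 55 | 4 | unchanged | no entry |
| 45 | 5 | worsened | no entry |

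**3. Would pooling on-oxygen values solve it?** No. Both documents use gradient = FiO2 × (Patm − 47) − PaCO2/0.8 − PaO2.
- Assume Patm 760, PaCO2 40 and an unchanged gradient of 45 mmHg. On room air PaO2 = 0.21 × 713 − 50 − 45 = 54.7 (DSS 4). At an assumed FiO2 of 0.28 it is 0.28 × 713 − 50 − 45 = 104.6 (DSS 1 or 2). Starting oxygen could be scored as improvement.
- Hold PaO2 at 60 instead. The gradient is 0.21 × 713 − 50 − 60 = 39.7 at FiO2 0.21 and 0.28 × 713 − 50 − 60 = 89.6 at 0.28.

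On-oxygen values should therefore be counted and shown separately, not pooled with room-air values.

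**4. How many subjects could lose their place?** Share without a shift category = k/n, where k is the number on oxygen at either visit. All k are assumed. Of the denominators only 60 (enrolled, SAP 3.2) comes from the documents; 20 is one arm if the three arms were equal.

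| k | n = 60 | n = 40 | n = 20 |
|---|---|---|---|
| 1 | 1.7% | 2.5% | 5.0% |
| 3 | 5.0% | 7.5% | 15.0% |
| 6 | 10.0% | 15.0% | 30.0% |

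To see what this could do to the table, take 60 subjects on room air at Visit 1, 6 of them later on oxygen, and about 20% of the other 54 worsened (11). The SAP table shows 11/54 = 20.4% worsened. If none of the six had worsened the share would be 11/60 = 18.3%; if all six had, (11 + 6)/60 = 28.3%. The SAP table cannot distinguish these cases.

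**5. PaO2.** SAP 7.2.1 summarises only the gradient. The blood gas tables are 14.2.1.1 and 14.2.1.2, both for (A-a)DO2, and the only blood gas figure is also for (A-a)DO2. No table, figure or listing title names PaO2. Its one role in a planned output is SAP 5.2, which counts PaO2 assessments missed because of the pandemic. DSS does not replace it: every PaO2 of 70 mmHg or more falls in category 1 or 2, separated only by symptoms.

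**6. Baseline.** SAP 7.2.6 compares with Visit 1, and the title of Table 14.2.6.2 with baseline. SAP 5.1 substitutes the closest IMPALA value when the baseline value is missing. Nothing says whether a Visit 1 score excluded for oxygen counts as missing.

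**The case against.** The best defence is that protocol 10.7.5 tells sites how to score and SAP 7.2.6 only decides what to display. Sites can follow the protocol fully, the scores remain in Listing 16.2.6.6, and protocol 11 leaves analysis detail to the SAP. DSS is defined on room air, and step 3 shows why mixing in on-oxygen values would mislead. This stands as a reason to keep the room-air display. It does not excuse leaving the choice undeclared when protocol 11 says all subjects are presented.

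It can also be said that the information is available elsewhere. SAP 5.1 shows missing counts where relevant, Table 14.1.2 gives subjects by visit, and Table 14.1.10 counts pandemic-related missed assessments. Tables 14.2.7.1 to 14.2.7.5 report oxygen use, and Tables 14.2.8.1 and 14.2.8.2 report aPAP status and treatment requirement by visit. These help, and a falling denominator would be noticed. None of them counts visits excluded for oxygen at sampling. SAP 7.2.7 works from concomitant medication, and a subject on long-term oxygen may still be sampled on room air, so the two counts need not agree.

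Three further points are fair. These are descriptive secondary outputs in an uncontrolled trial whose primary objective is safety. The baseline wording is a small matter, since Visit 1 is the Baseline visit. The percentages above only restate assumed counts and are not evidence of an effect.

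**Conclusion.** The concern holds and should be fixed. Four facts rest on the text alone: the DSS rules conflict, the SAP's choice is undeclared, the shift table has no category for moves onto or off oxygen at sampling, and PaO2 has no planned summary. The PaO2 gap is the plainest, because a named endpoint would go unsummarised.

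The (A-a)DO2 conflict is inferred, not explicit. The consequence for the results cannot be sized: its direction and amount depend on how many visits were sampled on oxygen, which the documents do not give. If few or none were, the DSS and (A-a)DO2 tables would hardly change. The PaO2 omission would remain whatever that number is.

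**What to change.** - Reconcile protocol 10.7.5 with SAP 7.2.6, and declare the DSS and (A-a)DO2 handling in SAP 9. Keep room air as the main display for both.
- Table 14.2.6.1: add a row for subjects on oxygen at sampling, outside the five-point scale.
- Table 14.2.6.2: add rows for room air to oxygen, oxygen to room air, and oxygen at both, with all assessed subjects in the denominator.
- (A-a)DO2 tables: give the number excluded for oxygen, by arm and visit.
- PaO2: add a by-visit table and a change-from-baseline table handled in the same way, or declare the omission in SAP 9.
- Baseline: state whether a Visit 1 value excluded for oxygen counts as missing under SAP 5.1, and use one reference term in SAP 7.2.6 and Table 14.2.6.2.

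The cost is SAP wording, a few table rows and two tables, all from data already collected. The drawback is longer tables with sparse cells, given 60 subjects over three arms. The new rows are also not an ordered scale, so reading them as better or worse needs judgement.
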